Protocol Amendment #8 (October 14, 2020)

J1651: A Phase 2 Study of Azacitidine in Combination with Pembrolizumab in Relapsed/Refractory Acute Myeloid Leukemia (AML) Patients and in Newly Diagnosed Older ( $\geq 65$  Years) AML Patients

Amendment #8 Incorporates:

X Administrative Protocol Revisions:

- Telemedicine options have been added to the protocol in the study calendar section (Section 6.1, page 56)

X Investigator's Brochure:

- Pembrolizumab IB edition 19
- The updated IB did not result in any changes to the study ICF.

Protocol Amendment #7 (January 14, 2020)

J1651: A Phase 2 Study of Azacitidine in Combination with Pembrolizumab in Relapsed/Refractory Acute Myeloid Leukemia (AML) Patients and in Newly Diagnosed Older ( $\geq 65$  Years) AML Patients

Amendment #7 Incorporates:

X Administrative Protocol Revisions:

- List of JH Co-Investigators updated
- Statement added to Section 5.1.1 reflecting study enrollment closure on 1/8/2020. The relapsed/refractory cohort has been completed, and new enrollment to the newly diagnosed AML cohort has been closed based on FDA guidance on the risk benefit analysis.
- Unit for albumin changed from mg/dL to g/dL in Section 5.1.2 Table 1

X Changes to the Informed Consent Form:

- Information added to section 2 to notify patients of enrollment closure and updated risk benefit analysis information from the FDA
- (Note: Risk language was previously updated with ICF template version 8-15-19 in accordance with Pembrolizumab IB v17 and aggregate safety report for Pembrolizumab Primary Adrenal Insufficiency. JHMIRB approved on 9-4-19.)

Protocol Amendment #6 (July 18, 2018)

J1651: A Phase 2 Study of Azacitidine in Combination with Pembrolizumab in Relapsed/Refractory Acute Myeloid Leukemia (AML) Patients and in Newly Diagnosed Older ( $\geq 65$  Years) AML Patients

Amendment #6 Incorporates:

X Changes to the Protocol:

- Correction of the spelling of pembrolizumab throughout the protocol
- An echocardiogram exception for screening has been added to section 7.1.5.1.1 and Section 6.1, footnote k. If an echocardiogram was conducted within 3 months prior to the screening date and the patient has not received any chemotherapy in the time between and has not experienced any cardiac symptoms or events (heart attack, chest pain, arrhythmia, etc), then the screening echocardiogram does not need to be repeated, unless it is clinically indicated per investigator's discretion.
- Vital signs will no longer be obtained post pembrolizumab infusion. This revision has been made to Section 6.1, footnote g.
- For pembrolizumab related toxicities, additional information about resumption of dosing has been added to Table 4 in Section 5.2.1.4.
- A window of 4 days has been added to the 30 day follow up visit in Section 6.1 so that the patients can be seen on their physicians' clinic days.
- The D-Dimer laboratory test has been removed from section 7.1.5.1.1.

X Changes to the Informed Consent Form to update the risk language as per new Pembrolizumab IBv16 and Merck recommendations, and include:

- The risk language in section 4 has been updated.
  - Statement added to indicate number of patients treated with pembrolizumab

- Statement under pembrolizumab risks was revised to note that immune-mediated adverse reactions may be fatal and may occur after discontinuation of pembrolizumab.
- Solid organ transplant risk information has been added.
- A new paragraph was included to note that “arthritis” was added after the Rare side effects section as an adverse reaction from the post-marketing environment.

Protocol Amendment #5 (January 23, 2018)

J1651: A Phase 2 Study of Azacitidine in Combination with Pembrolizumab in Relapsed/Refractory Acute Myeloid Leukemia (AML) Patients and in Newly Diagnosed Older ( $\geq 65$  Years) AML Patients

Amendment #5 Incorporates:

- Administrative changes to the protocol
  - Correcting name spelling of non-JHU co-investigator [name], Medical University of South Carolina, Hollings Cancer Center
- Changes to do the dose modification table for pembrolizumab-related immune adverse events in Section 5.2.1.4 according to Merck recommendations (letter dated 11/28/2017).
- Correction to the study calendar Section 6.1. to be consistent with footnotes and the intended collection schedule

## PROTOCOL AMENDMENT #4 (10/24/2017)

J1651: Phase 2 Study of Azacitidine in Combination with Pembrolizumab in Relapsed/Refractory Acute Myeloid Leukemia (AML) Patients and in Newly Diagnosed Older ( $\geq 65$  Years AML Patients)

AMENDMENT #4 INCORPORATES:  
X Administrative Changes to the Protocol

- Non-JHU co-investigator change from [name], PhD to [name]
- Clarification of cohort #2 exclusion criteria in Section 5.1.3

X Changes to the Informed Consent Form to update the risk language as per new Pembrolizumab IBv15 and Merck recommendations, and include:

- Addition of allogeneic stem cell transplant risk language
- Administrative changes

## PROTOCOL AMENDMENT #3 (08/17/2017)

### J1651: Phase 2 Study of Azacitidine in Combination with Pembrolizumab in Relapsed/Refractory Acute Myeloid Leukemia (AML) Patients and in Newly Diagnosed Older ( $\geq 65$ Years) AML Patients

This protocol is amended to update definition of disease response based on revisions included in AML European Leukemia Net criteria 2017 and provide clarification on the assessment of disease progression in accordance with AML ELN 2017, and expectations for response and follow up in AML patients undergoing low dose chemotherapy in combination with immunotherapy. The informed consent form is revised to update risk language for pembrolizumab according to a new version of the MK-3475 Risk Wording document issued on 06.09.2017 by Merck and Co.

#### AMENDMENT #3 INCORPORATES:

##### X Administrative, Editorial Changes to the Protocol

- Section 11.3 and 12 (Reference #63) revised to include online reference to revised AML criteria in 2017.
- Section 5.2.1.3 - corrected grammatical error, and section 5.2.1.4 –removed reference to Appendix, section 11.4 as it was incorrect.

##### X Scientific Changes to the Protocol

- Section 5.2.1.5.3- Added requirement that dose reductions/delays during cycle 1, 2 or subsequent cycles should be discussed with the Protocol Chair before being made.
- Section 7.1.2.6 – Response criteria were updated to reflect changes incorporated in new AML ELN criteria 2017. In particular, new categories for response assessment including complete remission without minimal residual disease (CRMRD-), morphologic leukemia-free state (MLFS), stable disease and molecular relapse were added. Also, definitions for response assessment (CR, CRi, PR, CD) were updated according to AML ELN 2017. In particular, progressive disease criteria were updated, with detailed clarification provided for follow up and subsequent treatment, as well as when patient should be removed from study for progressive disease before completion of 6 cycles of therapy.
- In accordance with updated response criteria (Section 7.1.2.6), changes to the section 1.0, section 2.1, section 3.3 (3. and 4.), section 4.2.3.1.2, 5.2.1.5.4, 7.1.5.5, 8.2.4, include adding morphologic leukemia-free state (MLFS) as a

- category of response; and minor changes to the section 1.0 (Duration of participation), section 2.1, section 5.2.1.3 to be consistent throughout the protocol, we changed wording to the bone marrow assessment.

## X Eligibility Changes

- Inclusion criterion (Section 5.1.2, Cohort #1 and #2, criterion 6.) changed to ECOG PS < 2 (previously  $\leq 2$ )

X Changes to the ICF to update the risk language for pembrolizumab according to a new version of the MK-3475 Risk Wording document issued on 06.09.2017 by Merck and Co. High level summary of changes:

### 1. General

- a. Wording of Rarely this condition can lead to death has been changed to Sometimes this condition can lead to death
- b. Changed the wording of some terms to align better with the other terms with regards to grammar and/or addition of symptoms upon Medical Director review.
- c. Removed KEYTRUDA® from document

### 2. What side effects could the study drug(s) cause?

- a. Section streamlined to remove specific reference to the approved indications by name as well as specific clinical trial exposure numbers, etc. as information changes continually.
- b. Added pembrolizumab information from patient medication guides (USPI medication guide and/or SmPC patient leaflet) to explain how pembrolizumab works and how it may cause side effects.
- c. Used the format of 4 categories (Very Common, Common, Uncommon, and Rare) which simplifies and eliminates need for repetition of terms by overall and serious frequencies, etc. vs percentages.
  - i. Removed duplicate terms, ie, that were in the previous version's Common and Serious side effect percentage categories
  - d. Removed reference to "immune-mediated" serious events <1%, as not helpful or informative for patient and has created numerous site/IRB/EC and Health Authority questions.
  - e. Added simplified language for 4 new terms: thyroiditis, myasthenic syndrome, sarcoidosis, and encephalitis.
3. Hematologic Malignancy trials language
  - a. Changed paragraph order and text for readability

## PROTOCOL AMENDMENT #2 (03/07/2017)

J1651: Phase 2 Study of Azacitidine in Combination with Pembrolizumab in Relapsed/Refractory Acute Myeloid Leukemia (AML) Patients and in Newly Diagnosed Older ( $\geq 65$  Years) AML Patients

AMENDMENT #2 INCORPORATES:

X Administrative Changes to the Protocol

- Clarified which type of tubes can be used for the specimen collection in the Section 6.1, 7.1.3.1.3.5., and 11.4.
- Provided additional clarification in the text for the Table 6.1 Study Flow Chart that the bone marrow should be obtained at the treatment discontinuation as well as PB and BM research specimens collected.
- Clarified that correlative studies will be done in collaboration with UNC (a participating site for this study), Section 7.1.3.1.3.

X Changes to the Informed Consent Form to update the risk language as per new Pembrolizumab IBv13 (02/17/2017) and Merck recommendations, and include:

- Administrative changes
- Update on the risks:
  - i. Additional language added to Severe Skin Reactions (first bullet) to reflect symptoms associated with Stevens-Johnson Syndrome and Toxic Epidermal Necrolysis.
  - ii. Diabetes language updated to ensure subjects know that they will likely need regular insulin
  - iii. New side effect language added for myocarditis (last bullet)
  - iv. New text for the potential side effect, myasthenic syndrome, has been added.

## PROTOCOL AMENDMENT #1 (12/28/2016)

J1651: Phase 2 Study of Azacitidine in Combination with Pembrolizumab in Relapsed/Refractory Acute Myeloid Leukemia (AML) Patients and in Newly Diagnosed Older ( $\geq 65$  Years) AML Patients

AMENDMENT #1 INCORPORATES:

Administrative Changes

Scientific Changes

Eligibility Changes

A summary of revisions is provided as follows:

1. Corrected language in Section 2.1 (page 8) to specify that patients will be assessed during cycle 1-3 for DLT to be consistent with the rest of the protocol.
2. Section 4.2.1. updated clinical results on use of anti-PD1 and azacitidine in AML.
3. Revised eligibility criteria (Section 5.2.1. Subject Inclusion Criteria) for Cohort #1 (4.), for Cohort #2 (4.) to allow prior treatment with hypomethylating agents.
4. Revised eligibility criteria (Section 5.2.2 Subject Exclusion Criteria) for Cohort #2 – Removed exclusion criteria (1.) to allow prior treatment with hypomethylating agents.
5. Revised Section 5.2.1.5 to be consistent with Section 5.2.1.4. specifying when delay in treatment between cycles will be allowed.
6. Revised Section 5.2.1.5.1 to better define circumstances when azacitidine treatment can be interrupted and restarted within a cycle.
7. Revised Section 6.1. Table footnote “a” to reflect changes listed under 5-6 of this amendment.
8. Revised Section 5.6.2 for hydroxyurea dosing during study.

**TITLE:** **Phase 2 Study of Azacitidine in Combination with Pembrolizumab in Relapsed/Refractory Acute Myeloid Leukemia (AML) Patients and in Newly Diagnosed Older (≥65 Years) AML Patients**

**Principal Investigator:** [name]  
(Study Chair)  
Sidney Kimmel Comprehensive Cancer Center (SKCCC) at  
Johns Hopkins  
[name]  
[name]  
[contact]; [contact]  
E-mail: [contact]

**Co-investigator(s):** [name]  
B. [name]  
[name], PhD  
[name]  
[name]  
[name]  
[name], PhD  
[name], PhD  
[name]  
[name], PhD

## 1.0 TRIAL SUMMARY

Abbreviated Title	Azacitidine and Pembrolizumab for the treatment of relapsed/refractory AML patients and newly diagnosed older ( $\geq 65$ years) AML patients who are not candidates for intensive induction chemotherapy
Trial Phase	Phase II
Clinical Indication	Safety Run In Phase (only Cohort 1): The treatment of relapsed and refractory AML patients with no prior history of allogeneic hematopoietic stem cell transplant (HSCT).  Phase 2: Cohort 1: The treatment of relapsed and refractory AML patients. Cohort 2: The treatment of newly diagnosed AML patients ( $\geq 65$ years) who are not candidates for intensive induction chemotherapy.
Trial Type	Interventional
Type of control	No control arm
Route of administration	Intravenous pembrolizumab; intravenous or subcutaneous azacitidine
Trial Blinding	Open Label
Treatment Groups	Cohort 1: Relapsed/refractory AML patients  Cohort 2: Newly diagnosed older patients ( $\geq 65$ years) who are not candidates for intensive induction chemotherapy
Number of trial subjects	Cohort 1: 10-40  Cohort 2: 10-40
Estimated enrollment period	24 months
Estimated duration of trial	48 months
Duration of Participation	Each subject will participate in the trial from the time the subject signs the Informed Consent Form through the final protocol-specified contact. Each treatment cycle will last 28 days. Bone marrow will be examined after 2 and 6 cycles and every 3-6 months thereafter. Patients who achieved complete remission (CR/CRI) or patients without remission but benefiting from therapy (partial remission [PR], morphologic leukemia-free state [MLFS], hematologic improvement [HI], stable disease [SD]) can continue on study receiving both azacitidine and pembrolizumab as long as they have ongoing clinical benefit without evidence of significant toxicity or disease progression and up to 2 years.
Estimated average length of treatment per patient	Up to 2 years or as long as subjects have ongoing clinical benefit without evidence of disease progression or significant toxicity.

## 2.0 TRIAL DESIGN

### 2.1 Trial Design

This is a multicenter, nonrandomized, open-label phase 2 study (with a safety run-in phase) of azacitidine (AZA) 75 mg/m^2 given IV or SQ on days 1-7 every 28 days in combination with pembrolizumab 200 mg given IV every 3 weeks (starting on day 8 of cycle 1). The dose/schedule of AZA selected for this study is FDA approved for patients with MDS/AML. The rationale for pembrolizumab dose/schedule- Section 4.2.2.

We plan to examine two AML patient cohorts:

**Cohort 1:** relapsed/refractory AML.

**Cohort 2:** newly diagnosed AML in older patients ( $\geq 65$  years) not candidates for induction chemotherapy.

Each cohort will be enrolled separately with distinct null hypotheses and statistical plans.

Azacitidine and pembrolizumab have distinct mechanisms of action with no common overlapping toxicities; however, as azacitidine and pembrolizumab have not been tested previously in combination in AML patients, we plan to start enrollment with **Cohort 1 (a safety run-in phase)** and include only relapsed/refractory AML patients excluding those relapsing after allogeneic hematopoietic stem cell transplant (alloHSCT).

**Cohort 1 (a safety run-in phase, 3 + 3 design):** The first three patients will be enrolled and receive planned azacitidine and pembrolizumab in cycle 1 (Section 2.2). If 0 or 1 patient of the first three patients have a DLT (dose limiting toxicity) in cycle 1, we will enroll additional 3 patients to better assess for toxicities. If less than 2 among first 6 patients experiences DLT in the cycle 1-3, we will open enrollment in Cohort 1 for all relapsed/refractory patients including those with prior history of alloHSCT and will also start to enroll patients in Cohort 2. We plan to monitor for DLTs up to the end of cycle 3 as some of immunological side effects associated with pembrolizumab may occur with the delay.

If  $\geq 2$  of the first 3 patients or  $\geq 2$  of 6 patients have DLTs during cycle 1, we will perform safety (detailed toxicity) review to assess for disease versus treatment-related toxicities. Given that pembrolizumab is given only once in cycle 1 (day 8), we will first dose de-escalate azacitidine to 75 mg/m^2 x 5 days. However, if the safety data analysis suggests that the toxicities are more likely pembrolizumab related, an alternative approach we may take is to exclude pembrolizumab in cycle 1 and start pembrolizumab dosing in cycle 2 when AML is better controlled but maintain azacitidine dose/schedule. If  $\leq 1$  of the 6 patients experience DLTs during cycle 1 but  $\geq 2$  of 6 patients experience DLTs during cycle 2 and cycle 3 or cycle 1, 2 and 3, we will first dose de-escalate pembrolizumab to 200 mg given every 4 weeks starting on Day 1 of Cycle 2 and maintain azacitidine dose/schedule. When each dose de-escalation occurs, additional 6 patients will be enrolled at that dose level. For the details of dose de-

[figure not shown]
escalation, please see Section 2.2 Trial Diagram.

Only after safe dose/schedule is defined ( $\leq 1$  of 6 patients having DLT in cycle 1-3) we will start enrollment in the phase 2 cohorts. A full safety assessment of the combination of AZA and pembrolizumab will be performed in all patients after 1, 2, and 3 cycles and in subsequent cycles according to the NCI Common Terminology Criteria for Adverse Events (CTCAE), version 4.0. For efficacy analysis, those patients who were treated at dose/schedule selected for Phase 2 will be included.

Bone marrow biopsy/aspirate will be performed after 2 and 6 cycles of therapy, and every 3-6 months thereafter as described in Section 6.0 Trial Flow Chart. Treatment with azacitidine/pembrolizumab will continue until confirmed disease progression, unacceptable toxicity, or if patient is withdrawn from study for other reasons (Section 5.9). Patients having a clinical benefit from this treatment combination including CR/CRI but also those who achieve response less than CR/CRI (ie., PR/MLFS/HI/SD) will be able to continue on treatment on clinical study (AZA and pembrolizumab) until they meet criteria specified in section 5.9. After the end of treatment, each subject will be followed for 30 days for AEs monitoring (serious adverse events will be collected for 90 days after the end of treatment as described in Section 7.2.3.3.2.). Subjects who discontinue treatment for reasons other than disease progression will have post-treatment follow up for disease status until disease progression, initiating non-study cancer treatment, withdrawing consent or becoming lost for follow up. All subjects will be followed for overall survival until death, withdrawal of consent or the end of the study, whichever comes first.

The primary objective of the run in safety phase would be to determine the safe and tolerable dose/schedule of azacitidine and pembrolizumab in patients with AML. We will perform safety run in phase only in Cohort 1 as Cohort 2 patients would be expected to have a same or better tolerability given that they are not heavily pretreated. Patients who relapse post alloHSCT will be enrolled on the study only if they are at least 3 month after alloHSCT and off all immune suppression for at least 3 weeks and have no evidence of active graft versus host disease (GVHD). These patients are expected to tolerate treatment as well as all other relapsed/refractory patients but will be monitored for any GVHD exacerbation in the course of treatment. The primary objective of this Phase 2 study would be to estimate the CR/CRI rates in two separate cohorts of patients: Cohort 1: relapsed or refractory AML patients. Cohort 2: Newly diagnosed older AML patients ( $\geq 65$  years) who are not candidates for intensive induction chemotherapy. Secondary objectives of the trial are to determine safety, tolerability, and analysis of various efficacy parameters such as overall response rate, disease-free survival, progression-free survival, time to progression, overall survival, and exploration of association between potential biomarkers and clinical activity. These analyses will be performed separately for each patient cohort.

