### 5.2.1.3 Dose Limiting Criteria

- Dose limiting toxicities during **safety run in phase** will be determined during Cycle 1, Cycle 2, and Cycle 3 of study treatment. Adverse events that occur after the first three cycles will also be evaluated by investigator and may be considered as dose limiting.
- Subjects with AML have frequently  $\geq$  grade 3 cytopenias; thus, will be un-evaluable for hematologic DLT with the exception listed below.
- For hematologic toxicity, the only adverse event that will be considered dose limiting is:
  - grade  $\geq$  4 neutropenia and thrombocytopenia with a hypocellular bone marrow and no evidence of residual leukemia lasting for 42 days

NOTE: only patients evaluable for hematologic toxicity as defined in Section 5.2.1.5.2.1, 5.2.1.5.2.3 and Section 5.2.1.5.3 may need to have a bone marrow assessment after cycle 1 if no count recovery to baseline. Otherwise, all patients will have bone marrow after cycle 2);

- For non-hematologic toxicities, the only adverse events that will be considered dose-limiting are:

- Any grade 4 toxicity considered at least possibly related to study drugs excluding asymptomatic electrolyte aberrations that can be corrected to  $\leq$  grade 2 and excluding specific toxicities that are frequent in AML population such as fever, infections, fatigue, bleeding, bone pain.
- Any grade 3 toxicity considered at least possibly related to study drugs that does not resolve to  $\leq$  grade 2 within 48 hours with the exception of Grade 3 anorexia, nausea, vomiting, diarrhea, or mucositis if it resolves to  $\leq$  grade 2 within 72 hours of maximal supportive care; asymptomatic electrolyte abnormalities that can be corrected to  $\leq$  grade 2 and excluding specific toxicities that are frequent in AML population such as fever, infections, fatigue, bleeding, bone pain. Grade 3 neurotoxicity and nephrotoxicity of any duration will be considered dose-limiting if at least possibly drug-related.

Table 3. Safety Run In Phase- Dose De-escalation Rules

Number of patients with DLT during run in phase (Planned 6 patients)	Decision rule
0 or 1 out of 3 in Cycle 1	Enter 3 more patients
$\geq$ 2 of 3 in Cycle 1 OR $\geq$ 2 of 6 in Cycle 1	Patients will be assessed for safety. Based on the complete assessment of AEs, the dose reduction as proposed in the Section 2.1 and 2.2.

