$\geq$ 2 of 6 in Cycle 2 or/and Cycle 3 OR $\geq$ 2 of 6 in Cycle 1+2+3	Patients will be assessed for safety. Based on the complete assessment of AEs, the dose reduction as proposed in the Section 2.1 and 2.2.
$\leq$ 1 of 6 in Cycle 1 + 2 + 3	Open Phase II Cohort 1 and Cohort 2.

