### **8.2 Statistical Analysis Plan**

#### **8.2.1 Safety Run-In**

Each cohort will be enrolled separately with distinct null hypotheses and statistical plans. Since azacitidine and pembrolizumab have not been tested previously in combination in AML patients, we plan first to start enrollment with Cohort 1 (a safety run-in phase). Recognizing that Cohort 1 may also include patients who relapsed after allogeneic hematopoietic stem cell transplant (alloHSCT) and thus may have differential sensitivity (tolerability, immune-related adverse events [IRAEs]) to this drug combination, we will start enrollment in Cohort 1 to include patients who did not have prior alloHSCT.

The primary objective of the safety run-in is to determine the safety and tolerability of AZA followed by pembrolizumab in relapsed and refractory AML using a 3+3 design. We plan to monitor for DLTs in cycles 1, 2 and 3 as some of immunological side effects associated with pembrolizumab may occur with the delay. The first three patients will be enrolled and receive planned azacitidine and pembrolizumab in cycle 1. If 0 or 1 patient of the first three patients has a DLT (dose limiting toxicity) in cycle 1, we will enroll an additional 3 patients to better assess for toxicities. If less than 2 among first 6 patients experiences DLT in the cycle 1-3, we will open enrollment in Cohort 1 for all relapsed/refractory patients including those with prior history of alloHSCT and will also start to enroll patients in Cohort 2. If  $\geq 2$  of the first 3 patients or  $\geq 2$  of 6 patients have DLTs during cycle 1, we will perform safety (detailed toxicity) review to assess for disease versus treatment-related toxicities. Given that pembrolizumab is given only once in cycle 1 (day 8), we will first dose de-escalate azacitidine as detailed in Section 2.2. However, if the safety data analysis suggests that the toxicities are more likely pembrolizumab related, an alternative approach we may take is to exclude pembrolizumab in cycle 1 and start pembrolizumab dosing in cycle 2 when AML is better controlled but maintain azacitidine dose/schedule as described in Section 2.2. If

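### Run-in patients 4-6 are entered on cycle 1 DLTs alone, so patients can be added to a level that two DLTs over cycles 1-3 have already ruled out

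*Combined protocol and SAP*

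**What the plan says.** **Entry of patients 4-6.** Section 2.1 (Trial Design): if 0 or 1 "of the first three patients have a DLT (dose limiting toxicity) in cycle 1, we will enroll additional 3 patients". Section 5.2.1.3, Table 3, attaches the decision to enter three more patients to "0 or 1 out of 3 in Cycle 1". Section 8.2.1 (Safety Run-In) has the same condition: if 0 or 1 "of the first three patients has a DLT (dose limiting toxicity) in cycle 1, we will enroll an additional 3 patients".

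**Passing a level.** Section 2.1: "If less than 2 among first 6 patients experiences DLT in the cycle 1-3, we will open enrollment in Cohort 1". In Table 3, at most 1 of 6 over cycles 1, 2 and 3 leads to "Open Phase II Cohort 1 and Cohort 2".

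**DLT window.** Section 2.1: "We plan to monitor for DLTs up to the end of cycle 3". The reason given is that some immune effects of pembrolizumab may be delayed.

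**Late DLTs.** The only stop with a denominator of three is for cycle 1. In Sections 2.1 and 8.2.1 and in Table 3, each trigger that counts cycle 2 or 3 DLTs has a denominator of six.

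**De-escalated levels.** Section 2.1: "When each dose de-escalation occurs, additional 6 patients will be enrolled at that dose level". Section 8.2.1 adds a maximum of two de-escalations. Both send the reader to the Section 2.2 diagram for details.

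**The concern.** Within a level, the decision to add patients and the decision to pass use different counts. A second DLT in any of cycles 1-3 makes at most 1 of 6 impossible, however many patients have been treated. If one of the first three has a DLT in cycle 1 and another has one in cycle 2, or if two have one in cycle 2, the written rule is still to enter three more.

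The gate is also weakest for the events that led to the longer window. It follows a single pembrolizumab dose, nominally on day 8. The only haematologic DLT has to last 42 days, so it cannot be confirmed by the end of a 28-day cycle.

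Up to three patients could be exposed at a level that can no longer be selected. Sections 2.1 and 8.2.1 restrict the efficacy analysis to the dose and schedule selected for phase 2, so these patients would not contribute to it.

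**Working it through.** **1. Figures in the plan.** The documents give no operating characteristics for the run-in. The nearest stated figure is the Section 8.2.2.1 toxicity rule, with a beta(0.5, 2) prior and a first look at 2 of 5 patients removed. The posterior is beta(0.5+2, 2+5-2) = beta(2.5, 5), and Pr(risk > 0.2) = 0.770 (stated: 0.77). The other seven posteriors also reproduce. That rule is correctly calculated, but it counts removals for toxicity, not DLTs.

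**2. Inputs.**
- From the documents: gate of at most 1 of 3 in cycle 1; pass criterion of at most 1 of 6 over cycles 1-3; 28-day cycles (Section 1.0); pembrolizumab once in cycle 1, on day 8 (Section 2.1), with delay allowed to day 22 (Section 5.10).
- Assumed: p, the cumulative DLT risk over cycles 1-3, from 0.1 to 0.5; f, the share of DLTs in cycle 1, from 1/3 to 2/3, with 1/6 as an extreme.

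Nominal follow-up from the pembrolizumab dose to the end of cycle 1 is 28 - 8 = 20 days, or 28 - 22 = 6 days after the permitted delay. Visit windows and cycle extensions can shift this.

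**3. Passing the gate with the level already lost.** Let T(x) = 3x²(1-x) + x³, the chance of at least 2 of 3. Failing the gate (at least 2 of 3 in cycle 1) is a subset of at least 2 of 3 over cycles 1-3, so the chance sought is T(p) - T(pf).

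Example with p = 0.3:
- T(0.3) = 3(0.09)(0.7) + 0.027 = 0.216.
- f = 1/3: T(0.1) = 0.027 + 0.001 = 0.028; difference 0.188.
- f = 2/3: T(0.2) = 0.096 + 0.008 = 0.104; difference 0.112.

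| p | T(p) | f = 2/3 | f = 1/2 | f = 1/3 | f = 1/6 |
|---|---|---|---|---|---|
| 0.1 | 0.028 | 0.015 | 0.021 | 0.025 | 0.027 |
| 0.2 | 0.104 | 0.055 | 0.076 | 0.091 | 0.101 |
| 0.3 | 0.216 | 0.112 | 0.155 | 0.188 | 0.209 |
| 0.4 | 0.352 | 0.177 | 0.248 | 0.303 | 0.339 |
| 0.5 | 0.500 | 0.241 | 0.344 | 0.426 | 0.480 |

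**4. Timing.** These are upper bounds on entering someone after two DLTs among the first three, since patients 4-6 may start before the second DLT occurs. Section 1.0 plans up to 40 Cohort 1 patients and 24 months of enrolment: 730/40 = about one patient every 18 days. A simulation used that fixed spacing, patient 4 starting when patient 3 finishes cycle 1, and DLT times uniform within cycle 1 or within cycles 2-3. The chance that at least one of patients 4-6 enters after two DLTs among the first three is about 10-17% at p = 0.3 and 15-28% at p = 0.4 (f from 2/3 to 1/6). Faster accrual lowers it. A second DLT arising in patient 4 or 5 is not counted.

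**5. Pass decision.** P(pass) = (1-p)⁶ + 6p(1-p)⁵ = 0.886, 0.655, 0.420, 0.233 and 0.109 for p = 0.1 to 0.5. Stopping entry at the second DLT leaves this unchanged, because the level has already failed.

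**6. What patients 4-6 can still influence.** Suppose the first three have one DLT in cycle 1 and one in cycle 2. A cycle 1 DLT in any of patients 4-6 takes the cycle 1 count to 2 of 6, which leads to a different de-escalation branch. Its chance is 1 - (1-pf)³. At p = 0.3 this is 14%, 27% and 49% for f = 1/6, 1/3 and 2/3; at p = 0.4 it is 19%, 35% and 61%.

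**The case against.** **Entry is centrally controlled.** A treatment slot is confirmed before a subject is approached (Section 7.1.1.6), adverse events are reviewed at least every two weeks (7.2.3.1), safety is assessed after cycles 1, 2 and 3 (2.1), and toxicity is monitored after every five patients (8.2.2.1). In practice, someone might well pause entry. But the first three carry no stated rule on DLTs and entry. The fourth counts removals, does not separate dose levels, and does not say how run-in patients count.

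**The added patients are not uninformative.** A reader might infer that their data cannot affect any decision. That goes too far. Section 2.1 uses the cycle 1 count among six patients to steer which drug is reduced first, and step 6 shows that this count can change. Only the pass decision is beyond their influence.

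**De-escalated levels.** A reader might infer that six patients are entered there with no interim check. The text states no three-patient step, but the Section 2.2 diagram is not available for this review. Table 3 is titled as the run-in de-escalation rules, and its three-patient row is not limited to the first level. The inference cannot be established.

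**The run-in is over.** Section 5.1.1 says Cohort 1 has enrolled its 40 patients, so new wording protects no one in this trial. This stands, and it determines what can usefully be done now.

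**Conclusion.** The concern holds for entry of patients 4-6. Sections 2.1 and 8.2.1 and Table 3 consistently use cycle 1 alone for that step and cycles 1-3 for passing, and nothing else in the documents closes the gap.

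Its size rests on an assumed DLT risk and timing. With one third to two thirds of DLTs in cycle 1, the upper bounds run from about 2% at a 10% risk, through 5.5-9% at 20% and 18-30% at 40%, to 24-43% at 50%. With only one sixth in cycle 1, they reach 21%, 34% and 48% at 30%, 40% and 50%. At the planned accrual pace the problem shrinks but does not disappear. For a tolerable regimen it is small.

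The consequence is avoidable exposure. A reader might infer that too toxic a level could be passed, or that patients in this trial were in fact entered after two DLTs. The first is excluded by the arithmetic, and the documents do not report the run-in DLTs needed to judge the second.

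**What to change.** Reconcile Sections 2.1 and 8.2.1 and Table 3:

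- Base the decision to add patients within a level on the same cycle 1-3 DLT count as the pass criterion, taken over all patients treated so far at that level. A second DLT sends the level to the safety review already described before anyone else is entered.
- State how the existing de-escalation branches, which are written for six patients, apply when a level is reviewed with fewer. No dose step is proposed here.
- Confirm that the Section 2.2 diagram, Table 3 and the text agree on whether the three-patient step applies at de-escalated levels.

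Because Cohort 1 is complete, the present action is to correct the wording for any reuse of the design and to state in the report which DLTs were known, and which governed, at each run-in entry.

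The cost is protocol wording and a short reporting item. No pass decision changes. The downside is less toxicity data on a level that cannot be selected, and less information on the cycle 1 count that steers which drug is reduced first.
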